4.1. Inclusion Criteria

To be enrolled in the study, each potential subject must satisfy all of the following inclusion criteria.

Disease Related

Metastatic renal cell cancer patients (any histologic subtype) with measurable and/or evaluable disease who have completed at least one line of prior systemic therapy are potentially eligible for this trial. Any number of prior systemic therapies are allowed, including prior nivolumab.

Laboratory

1. Adequate hematologic function defined as:
 - Absolute neutrophil count $>750 \text{ cells/mm}^3 (0.75 \times 10^9/\text{L})$.
 - Platelet count $>50,000 \text{ cells/mm}^3 (50 \times 10^9/\text{L})$.
 - Hemoglobin $>8.0 \text{ g/dL}$.
2. Adequate hepatic and renal function defined as:
 - Serum aspartate transaminase (AST) or alanine transaminase (ALT) $\leq 3.0 \times$ upper limit of normal (ULN).
 - Estimated Creatinine Clearance $\geq 30 \text{ ml/min}$ (Cockcroft-Gault)
 - Bilirubin $\leq 1.5 \times$ ULN (unless bilirubin rise is due to Gilbert's syndrome or of non-hepatic origin)
3. PT/INR $<1.5 \times$ ULN and PTT (aPTT) $<1.5 \times$ ULN.

Demographic

4. Men and women ≥ 18 years of age.
5. Eastern Cooperative Oncology Group (ECOG) performance status of 0-2.

Ethical/Other

6. Female subjects who are of non-reproductive potential (ie, post-menopausal by history - no menses for ≥ 1 year; OR history of hysterectomy; OR history of bilateral tubal ligation; OR history of bilateral oophorectomy). Female subjects of childbearing potential must have a negative serum pregnancy test upon study entry.
7. Male and female subjects who agree to use both a highly effective methods of birth control (eg, implants, injectables, combined oral contraceptives, some intrauterine devices [IUDs], sexual abstinence, or sterilized partner) and a barrier method (eg, condoms, cervical ring, sponge, etc) during the period of therapy and for 30 days after the last dose of study drug

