4.2. Exclusion Criteria

To be enrolled in the study, potential subjects must meet NONE of the following exclusion criteria:

Concurrent Conditions

1. Cytotoxic chemotherapy \leq 21 days prior to first administration of study treatment and/or monoclonal antibody \leq 4 weeks prior to first administration of study treatment and/or other RCC-directed systemic therapy \leq 2 weeks prior to first administration of study treatment
2. Any known additional malignancy that is progressing or requires active treatment. Exceptions include basal cell carcinoma of the skin, squamous cell carcinoma of the skin, or in situ cervical cancer that has undergone potentially curative therapy.
3. Concurrent systemic immunosuppressant therapy (eg, cyclosporine A, tacrolimus, etc., or chronic administration [>14 days] of >10 mg/day of prednisone) within 28 days of the first dose of study drug.
4. Vaccinated with live, attenuated vaccines within 4 weeks of first dose of study drug.
5. Recent infection requiring systemic treatment that was completed \leq 14 days before the first dose of study drug.
6. Unresolved toxicities from prior anti-cancer therapy, defined as having not resolved to Common Terminology Criteria for Adverse Event (CTCAE, version 4), grade \leq 1, or to the levels dictated in the inclusion/exclusion criteria with the exception of alopecia.
7. Known bleeding disorders (eg, von Willebrand's disease) or hemophilia.
8. History of stroke or intracranial hemorrhage within 6 months prior to enrollment.
9. Known history of human immunodeficiency virus (HIV) or active with hepatitis C virus (HCV) or hepatitis B virus (HBV). *Subjects who are positive for hepatitis B core antibody or hepatitis B surface antigen must have a negative polymerase chain reaction (PCR) result before enrollment. Those who are PCR positive will be excluded.*
10. Any uncontrolled active systemic infection.
11. Major surgery within 4 weeks of first dose of study drug.
12. Any life-threatening illness, known autoimmune disease, medical condition, or organ system dysfunction that, in the investigator's opinion, could compromise the subject's safety or put the study outcomes at undue risk.

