13. Currently active, clinically significant cardiovascular disease, such as uncontrolled arrhythmia or Class 3 or 4 congestive heart failure as defined by the New York Heart Association Functional Classification; or a history of myocardial infarction, unstable angina, or acute coronary syndrome within 6 months prior to enrollment.
14. Unable to swallow capsules or malabsorption syndrome, disease significantly affecting gastrointestinal function, or resection of the stomach or small bowel, symptomatic

inflammatory bowel disease or ulcerative colitis, or partial or complete bowel obstruction.

15. Lactating or pregnant.
16. Unwilling or unable to participate in all required study evaluations and procedures.
17. Unable to understand the purpose and risks of the study and to provide a signed and dated informed consent form (ICF) and authorization to use protected health information (in accordance with national and local subject privacy regulations).
18. Concomitant use of warfarin or other Vitamin K antagonists. Note: Subjects receiving antiplatelet agents in conjunction with ibrutinib should be observed closely for any signs of bleeding or bruising, and ibrutinib should be withheld in the event of any bleeding events. Supplements such as fish oil and vitamin E preparations should be avoided.
19. Requires treatment with a strong cytochrome P450 (CYP) 3A4/5 inhibitor. (see Appendix 3)
20. QT prolongation and/or familiar history of QT prolongation and uncontrolled cardiac arrhythmias that in the opinion of the investigator would interfere with the patient's safety or compliance on trial.
21. Currently active, clinically significant hepatic impairment Child-Pugh class B or C according to the Child Pugh classification (Appendix 10).

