5.3.4. Guidelines for Dosage Modification and Treatment Interruption or Discontinuation

Nivolumab treatment will be given for up to one year.

Patients may temporarily suspend study treatment for up to 42 days from the last dose if they experience toxicity that is considered related to the study drug and requires a dose to be held. If nivolumab is held because of adverse events for >42 days beyond the last dose, then the patient will be discontinued from nivolumab.

If a patient must be tapered off steroids used to treat adverse events, nivolumab may be held for additional time beyond 42 days from the last dose until steroids are discontinued or reduced to prednisone dose (or dose equivalent) ≤ 10 mg/day. The acceptable length of interruption will depend on an agreement between the investigator and the Principal Investigator.

Dose interruptions for reason(s) other than toxicity, such as surgical procedures, may be allowed with Principal Investigator approval. The acceptable length of interruption will depend on agreement between the investigator and the Principal Investigator.

Any toxicities associated or possibly associated with nivolumab treatment should be managed according to standard medical practice. Additional tests, such as autoimmune serology or biopsies, may be used to determine a possible immunogenic etiology.

Patients should be assessed clinically (including review of laboratory values) for toxicity prior to, during, and after each infusion. If unmanageable toxicity due to nivolumab occurs at any time during the study, treatment with nivolumab should be discontinued.

Management of potential immune related AEs are described in the following sections.

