5.3.4.3. Hepatotoxicity

Immune-mediated hepatitis has occurred with the administration of nivolumab.

Patients should be monitored for abnormal liver tests prior to and periodically during treatment. While on this study, patients presenting with right upper-quadrant abdominal pain and/or unexplained nausea or vomiting should have LFTs performed immediately and LFTs should be reviewed before administration of the next dose of study drug.

If LFTs increase, neoplastic, concurrent medications, viral hepatitis, and toxic etiologies should be considered and addressed, as appropriate. Imaging of the liver, gall bladder, and biliary tree should be performed to rule out neoplastic or other causes for the increased LFTs. Anti-nuclear antibody, perinuclear anti-neutrophil cytoplasmic antibody, anti-liver-kidney microsomal antibodies, and anti-smooth muscle antibody tests should be performed in an autoimmune etiology is considered.

Patients with LFT abnormalities should be managed according to the guidelines in Table 3.

Table 3 Dose Modification Guidelines for Hepatotoxicity

Symptoms	Management	Follow-up
Grade 1: AST or ALT >ULN to 3xULN and/or T Bili >ULN to 1.5xULN	Continue nivolumab Regularly monitor LFTs	Continue monitoring LFTs
Grade 2: AST or ALT >3 to \leq 5 x ULN and/or T Bili >1.5 to \leq 3 ULN	
 - Withhold nivolumab - Increase frequency of monitoring to every 3 days - 1 to 2 mg/kg/day prednisone equivalents 	If improved to Grade 1 or baseline, resume nivolumab. If steroids have been administered, taper steroids over at least 1 month before resuming nivolumab. Resume routine LFT monitoring
Grade 3 or 4: AST or ALT >5x ULN and/or T Bili >3x ULN	
 - Permanently discontinue nivolumab - Increase frequency of monitoring to every 1-2 days - Gastroenterology consult - Treat with 1-2 mg/kg/day prednisone equivalent 	If improved to <Grade 2, taper steroids over at least 1 month If labs persist >3-5 days, worsen or rebound: add non-corticosteroid immunosuppressive medication

IV = intravenous; LFT = liver function test; ULN = upper limit of normal.

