Appendix 10: Child-Pugh Score

Measure	1 point	2 points	3 points
Total bilirubin, μ mol/L (mg/dL)	<34 (<2)	34-50 (2-3)	>50 (>3)
Serum albumin, g/L (g/dL)	>35 (>3.5)	28-35 (2.8-3.5)	<28 (<2.8)
PT INR	<1.7	1.71-2.30	>2.30
Ascites	None	Mild	Moderate to Severe
Hepatic encephalopathy	None	Grade I-II (or suppressed with medication)	Grade III-IV (or refractory)

Points	Class
5-6	A
7-9	B
10-15	C

Source:

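### The transaminase entry limit is joined by *or*, so read literally one enzyme at or below 3.0 × ULN is enough, although the evident intent is that neither may exceed it

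*Combined protocol and SAP*

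**What the plan says.** Inclusion criterion 2 in Section 4.1 defines adequate hepatic function partly by "Serum aspartate transaminase (AST) or alanine transaminase (ALT"), with a ceiling of 3.0 × ULN. The synopsis uses the same wording, so it does not settle the reading. The next laboratory item in Section 4.1 joins its two ceilings, PT/INR and PTT, with *and*.

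Three exclusions in Section 4.2 could also bear on liver enzymes:

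- Exclusion 6 concerns toxicity left over from earlier anti-cancer treatment. It asks for resolution to CTCAE grade 1 or lower, "or to the levels dictated in the inclusion/exclusion criteria with the exception of alopecia".
- Exclusion 12 leaves illness or organ dysfunction to the investigator's opinion.
- Exclusion 21 reads "Currently active, clinically significant hepatic impairment Child-Pugh class B or C according to the Child Pugh classification", scored by Appendix 10.

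Table 3 in Section 5.3.4.3 governs nivolumab on study. Its Grade 1 row is "AST or ALT >ULN to 3xULN and/or T Bili >ULN to 1.5xULN" (continue). Its Grade 2 row covers AST or ALT above 3 and up to 5 × ULN (withhold). Its Grade 3 or 4 row is "AST or ALT >5x ULN and/or T Bili >3x ULN" (permanently discontinue).

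**The concern.** The word *or* does different work in a floor and in a ceiling. In a trigger such as above 5 × ULN, *or* means that either enzyme sets it off, which is the cautious direction. In an upper limit for entry, the same word means that either enzyme being low enough satisfies it, which is the permissive direction.

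The limit is an operative safety threshold. Ibrutinib is metabolized in the liver (Section 5.3.1.5) and nivolumab has caused immune-mediated hepatitis (Section 5.3.4.3). Applied exactly as written, the rule would admit a patient with one enzyme at a level where the trial's own table withholds or stops nivolumab. Sites should also be able to rely on the text for a uniform reading, and the second site was still to be determined (Section 3.2.1).

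**Working it through.** The plan gives no figure on this point to reproduce. The check compares the two readings and then looks for any other numeric limit on AST or ALT.

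**1. The two readings, in multiples of ULN.** As written: eligible if min(AST, ALT) ≤ 3.0. As evidently intended: eligible if max(AST, ALT) ≤ 3.0.

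| AST | ALT | min | max | As written | Both ≤ 3.0 | Table 3 range of the worse enzyme |
|---|---|---|---|---|---|---|
| 2 | 2 | 2 | 2 | eligible | eligible | Grade 1 |
| 4 | 2.5 | 2.5 | 4 | eligible | not eligible | Grade 2, withhold |
| 6 | 2.5 | 2.5 | 6 | eligible | not eligible | Grade 3 or 4, discontinue |
| 4 | 4 | 4 | 4 | not eligible | not eligible | Grade 2, withhold |

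The readings differ only when one enzyme is within 3.0 and the other above it. These are illustrative values, not observed patients.

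**2. Does another criterion cap the second enzyme?**

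- *Exclusion 6.* The grade 1 limb helps: Table 3 tops Grade 1 at 3 × ULN, and every patient has had prior systemic therapy. It reaches only toxicity from that therapy, however, and not other causes such as liver metastases. Its alternative limb also refers back to the entry levels and so to the same *or*.
- *Exclusion 12.* It is a matter of opinion and gives no number.
- *Exclusion 21.* The Child-Pugh score has five components: bilirubin, albumin, INR, ascites and encephalopathy. Assume bilirubin below 2 mg/dL, albumin above 3.5 g/dL, INR below 1.7 and neither ascites nor encephalopathy. Either mixed example then scores 1 + 1 + 1 + 1 + 1 = 5 points, which is class A (5 to 6) and not excluded.
- *The bilirubin and coagulation limits.* They do not constrain AST or ALT.

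**3. What was meant?** Entry at 3.0 × ULN for AST/ALT and 1.5 × ULN for bilirubin equals the top of Table 3's Grade 1 row on both measures. If *or* in Table 3 were read by the lower enzyme where that suits, AST 6 with ALT 2.5 would fall in the Grade 1 and the Grade 3 or 4 rows at once, with contradictory instructions. The table makes sense only if graded by the worse enzyme. Carried to entry, that usage means neither enzyme may exceed 3.0.

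**4. Effect on the statistics.** The rule of 15 or more out of 25 gives an exact one-sided level of 0.0344 at 40% and power of 0.902 at 70%. This agrees with the stated 0.034 and 90% in Section 10.3. None of these inputs involves the enzyme criterion.

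**The case against.** The strongest reply is that nobody would apply the literal reading. The protocol uses the phrase as shorthand for whichever transaminase is worse, the criterion is headed as adequate organ function, and an AST of 6 × ULN plainly is not that. This stands as evidence of intent, but it does not put the intent into the rule.

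The second reply is that the safeguards are real. Section 5.3.4.3 calls for liver tests before as well as during treatment, and sends abnormalities to Table 3. Section 5.3.4 adds "Patients should be assessed clinically (including review of laboratory values) for toxicity prior to, during, and after each infusion". Section 8.2.1 repeats serum chemistry and the eligibility check on Cycle 1 Day 1. Appendix 7 has a coordinator verify every registration and directs eligibility questions to the coordinating site. These make a wrongful enrolment rare. The Day 1 check and central verification, however, test patients against the written criterion, so they do not supply the missing word.

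Three stronger inferences are tempting, and the documents support none of them:

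- *That a one-enzyme rule was chosen deliberately.* Nothing says so, and the match with Table 3 points the other way.
- *That nothing else limits the second enzyme.* Exclusion 6 does so in part.
- *That enrolment would directly contradict Table 3.* Section 5.3.4 introduces these tables with "Management of potential immune related AEs are described in the following sections", so they address immune-related events rather than entry. Table 3 is used here to show what the enzyme levels mean clinically and what the limit was meant to match.

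**Conclusion.** The point holds as a minor wording error in an operative safety criterion. It is not a design choice. Followed exactly, the text admits patients with one enzyme above 3.0 × ULN, and exclusion 6 closes that gap only in part.

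The conclusion rests on the literal wording in both places and on the absence of any other firm numeric limit on AST or ALT. The examples assume that the other liver measures are normal. The documents give no frequency for such patients. With the safeguards it should be rare, and no percentage is claimed. The primary endpoint, the decision rule and the sample size are unaffected.

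**What to change.** In Section 4.1 and in the synopsis, replace the present wording with: *AST and ALT both ≤ 3.0 × ULN*. Exclusion 6 then needs no edit, because its reference back to the entry levels will point to an unambiguous limit.

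The cost is one line in two places. The only downside is the rare exclusion of a patient with one enzyme above the limit, whom the criterion was evidently meant to exclude.

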4.2. Exclusion Criteria

To be enrolled in the study, potential subjects must meet NONE of the following exclusion criteria:

Concurrent Conditions

1. Cytotoxic chemotherapy \leq 21 days prior to first administration of study treatment and/or monoclonal antibody \leq 4 weeks prior to first administration of study treatment and/or other RCC-directed systemic therapy \leq 2 weeks prior to first administration of study treatment
2. Any known additional malignancy that is progressing or requires active treatment. Exceptions include basal cell carcinoma of the skin, squamous cell carcinoma of the skin, or in situ cervical cancer that has undergone potentially curative therapy.
3. Concurrent systemic immunosuppressant therapy (eg, cyclosporine A, tacrolimus, etc., or chronic administration [>14 days] of >10 mg/day of prednisone) within 28 days of the first dose of study drug.
4. Vaccinated with live, attenuated vaccines within 4 weeks of first dose of study drug.
5. Recent infection requiring systemic treatment that was completed \leq 14 days before the first dose of study drug.
6. Unresolved toxicities from prior anti-cancer therapy, defined as having not resolved to Common Terminology Criteria for Adverse Event (CTCAE, version 4), grade \leq 1, or to the levels dictated in the inclusion/exclusion criteria with the exception of alopecia.
7. Known bleeding disorders (eg, von Willebrand's disease) or hemophilia.
8. History of stroke or intracranial hemorrhage within 6 months prior to enrollment.
9. Known history of human immunodeficiency virus (HIV) or active with hepatitis C virus (HCV) or hepatitis B virus (HBV). *Subjects who are positive for hepatitis B core antibody or hepatitis B surface antigen must have a negative polymerase chain reaction (PCR) result before enrollment. Those who are PCR positive will be excluded.*
10. Any uncontrolled active systemic infection.
11. Major surgery within 4 weeks of first dose of study drug.
12. Any life-threatening illness, known autoimmune disease, medical condition, or organ system dysfunction that, in the investigator's opinion, could compromise the subject's safety or put the study outcomes at undue risk.
13. Currently active, clinically significant cardiovascular disease, such as uncontrolled arrhythmia or Class 3 or 4 congestive heart failure as defined by the New York Heart Association Functional Classification; or a history of myocardial infarction, unstable angina, or acute coronary syndrome within 6 months prior to enrollment.
14. Unable to swallow capsules or malabsorption syndrome, disease significantly affecting gastrointestinal function, or resection of the stomach or small bowel, symptomatic

inflammatory bowel disease or ulcerative colitis, or partial or complete bowel obstruction.

15. Lactating or pregnant.
16. Unwilling or unable to participate in all required study evaluations and procedures.
17. Unable to understand the purpose and risks of the study and to provide a signed and dated informed consent form (ICF) and authorization to use protected health information (in accordance with national and local subject privacy regulations).
18. Concomitant use of warfarin or other Vitamin K antagonists. Note: Subjects receiving antiplatelet agents in conjunction with ibrutinib should be observed closely for any signs of bleeding or bruising, and ibrutinib should be withheld in the event of any bleeding events. Supplements such as fish oil and vitamin E preparations should be avoided.
19. Requires treatment with a strong cytochrome P450 (CYP) 3A4/5 inhibitor. (see Appendix 3)
20. QT prolongation and/or familiar history of QT prolongation and uncontrolled cardiac arrhythmias that in the opinion of the investigator would interfere with the patient's safety or compliance on trial.
21. Currently active, clinically significant hepatic impairment Child-Pugh class B or C according to the Child Pugh classification (Appendix 10).

5. TREATMENT OF SUBJECTS

5.1. Treatment allocation and blinding (if appropriate)

N/A

5.2. Study treatment

This will be a non-randomized open-label prospective phase 1b/II study of the combination of ibrutinib with nivolumab in mRCC. See Section 3.1.1 Study Schema.

5.2.1. Route and schedule

Repeat every 28 days

Dose Level	Nivolumab dose	Ibrutinib dose (days 1-28)*
Level 0	240 mg IV q2 weeks	560mg PO
Level -1	240 mg IV q2 weeks	420mg PO

*should be taken at the same time every day

Dose limiting toxicity (DLT) must be treatment-related (possibly, probably, or definitely). To be evaluable for DLT, the subject must have had one dose of Nivolumab and at least 3 weeks of Ibrutinib.

Dose limiting toxicity (DLT) is defined as:

- 1) Grade 4 absolute neutrophil count with fever (>101.4 F) or documented infection;
- 2) Grade 4 thrombocytopenia or Grade 3 thrombocytopenia with bleeding;
- 3) Any grade 3 or greater non-hematologic toxicity excluding alopecia.

DLT will be assessed after 1 cycle (4 weeks).

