3.1.1. Study Schema

*DLT assessment after 1 cycle (4 weeks)

*DLT = Grade III or higher SAE attributed to treatment

**Patients will have two de-escalation dose levels for (-1 and -2) for all patients based on interim toxicities.

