5.3.1.4. Dose Modification for Adverse Reactions

The dose of study drug should be modified according to the dose modification guidelines in Table 1 if any of the following toxicities occur:

- Grade 4 ANC (<500/ μ L) for more than 7 days or fibroneutropenia.
- Grade 3 thrombocytopenia (<50,000/ μ L) in the presence of clinically significant bleeding events.
- Grade 4 thrombocytopenia (<25,000/ μ L).
- Grade 3 or 4 nausea, vomiting, or diarrhea if persistent, despite optimal anti-emetic and/or anti-diarrheal therapy.
- Any other Grade 4 or unmanageable Grade 3 toxicity.

For Grade 3 or 4 atrial fibrillation or persistent atrial fibrillation of any grade, consider the risks and benefits of ibrutinib treatment. If clinically indicated, the use of anticoagulants or antiplatelet agents may be considered for the thromboprophylaxis of atrial fibrillation (Section 6.2.4).

Note: After a dose reduction, dose escalation of ibrutinib to a previous higher dose is NOT allowed.

Table 1. Ibrutinib Dose Modifications

Occurrence	Action to be Taken
First	Withhold study drug until recovery to Grade ≤ 1 or baseline; may restart at original dose level
Second	Withhold study drug until recovery to Grade ≤ 1 or baseline; may restart at 1 dose level lower (ie, 280 mg/day for 420 mg/day dose; 420 mg/day for 560 mg /day dose)
Third	Withhold study drug until recovery to Grade ≤ 1 or baseline; may restart at 1 dose level lower (ie, 140 mg/day for 420 mg/day dose; 280 mg/day for 560 mg /day dose)
Fourth	Discontinue study drug

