11.1.2. Serious Adverse Events

A serious adverse event based on ICH and EU Guidelines on Pharmacovigilance for Medicinal Products for Human Use is any untoward medical occurrence that at any dose:

- Results in death (ie, the AE actually causes or leads to death).
- Is life-threatening. Life-threatening is defined as an AE in which the subject was at risk of death at the time of the event. It does not refer to an event which hypothetically might have

caused death if it were more severe. If either the Investigator or the IND Sponsor believes that an AE meets the definition of life-threatening, it will be considered life-threatening.

- Requires in-patient hospitalization >24 hours or prolongation of existing hospitalization.
- Results in persistent or significant disability/incapacity (ie, the AE results in substantial disruption of the subject's ability to conduct normal life functions).
- Is a congenital anomaly/birth defect.
- Is an important medical event that may not result in death, be immediately life-threatening or require hospitalization, but may be considered an SAE when, based upon appropriate medical judgment, the event may jeopardize the subject or subject may require intervention to prevent one of the other outcomes listed in this definition. Examples of such events are intensive treatment in an emergency department or at home for allergic bronchospasm, blood dyscrasias, or convulsion that does not result in hospitalization; or development of drug dependency or drug abuse.

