11.1.4. Causality (Attribution)

The Investigator is to assess the causal relation (ie, whether there is a reasonable possibility that the study drug caused the event) using the following definitions:

Not Related (unrelated): Another cause of the AE is more plausible; a temporal sequence cannot be established with the onset of the AE and administration of the investigational product; or, a causal relationship is considered biologically implausible.

Unlikely: The current knowledge or information about the AE indicates that a relationship to the investigational product is unlikely.

Possibly Related: There is a clinically plausible time sequence between onset of the AE and administration of the investigational product, but the AE could also be attributed to concurrent or underlying disease, or the use of other drugs or procedures. Possibly related should be used when the investigational product is one of several biologically plausible AE causes.

Related: The AE is clearly related to use of the investigational product.

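### Sections 3.1.1 and 5.2.1 define DLT differently, and the 3-week ibrutinib minimum has no visible exception for a DLT that itself interrupts ibrutinib

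*Combined protocol and SAP*

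**What the plan says.** Two places define DLT, both with a one-cycle (4-week) window.

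- **Section 3.1.1, schema footnote:** "DLT = Grade III or higher SAE attributed to treatment". A second footnote provides for "de-escalation dose levels for (-1 and -2) for all patients based on interim toxicities".
- **Section 5.2.1:** three items, none requiring seriousness. The first is Grade 4 neutropenia with fever or a documented infection. The second is thrombocytopenia of Grade 4, or of Grade 3 with bleeding. The third is "Any grade 3 or greater non-hematologic toxicity excluding alopecia". On attribution it says "Dose limiting toxicity (DLT) must be treatment-related (possibly, probably, or definitely".

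Section 5.2, the parent of 5.2.1, refers the reader to the 3.1.1 schema, so both texts are presented as current.

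On who counts, Section 5.2.1 says: "To be evaluable for DLT, the subject must have had one dose of Nivolumab and at least 3 weeks of Ibrutinib".

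Three other sections bear on this:

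- Section 11.1.2 makes seriousness a separate test from grade; one criterion is "Requires in-patient hospitalization >24 hours or prolongation of existing hospitalization".
- Section 11.1.4 gives the investigator four causality categories: not related, unlikely, possibly related and related. The last is worded "Related: The AE is clearly related to use of the investigational product". There is no probable or definite category.
- Section 5.3.1.4 with Table 1 withholds ibrutinib for Grade 4 thrombocytopenia, for Grade 3 thrombocytopenia "in the presence of clinically significant bleeding events", and for other Grade 4 or unmanageable Grade 3 toxicity, among others. Section 9.2 ends study treatment for unacceptable toxicity.

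**The concern.** With two definitions in force, two sites, or the same team at two times, can classify the same event differently. The direction of the resulting error is not fixed, because each definition captures events that the other misses.

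The evaluability sentence raises a different problem. A minimum exposure is meant to keep subjects with too little drug from counting as tolerating it. Applied without an exception, it also removes a subject whose exposure was short because of the DLT. The toxicities that matter most to the count are then the ones most likely to drop out of it. DLT is the only defined cycle-1 tolerability measure in the readable text, in a trial whose primary objective includes feasibility.

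**Working it through.** **1. The plan's own figure.** The only operating characteristic in the readable text is the efficacy rule in Section 10.3: 15 or more of 25 progression-free at 6 months, 40% against 70%. The exact binomial gives a one-sided level of 0.0344 and power of 0.902, matching the stated 0.034 and 90%. That rule does not use DLT status and is not in question here.

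**2. The two definitions side by side.**

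| Event, treatment-related, in cycle 1 | Section 3.1.1 | Section 5.2.1 |
|---|---|---|
| Grade 3 ALT rise meeting no criterion in 11.1.2 | Not a DLT (not serious) | DLT (third item) |
| Grade 3 anemia meeting a criterion in 11.1.2 | DLT | Not a DLT (hematologic, but neither neutrophils nor platelets) |

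Each column contains a DLT that the other lacks, so the definitions are not nested. Reading the footnote's seriousness term as a slip for any adverse event would not help: every related Grade 3 anemia would then be a DLT under 3.1.1 and still not under 5.2.1.

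**3. When the 3-week minimum is missed.** Assume that 3 weeks means 21 dosing days (the protocol does not say), that dosing is daily from day 1, and that no other doses are missed. A hold starting on day *d* follows *d* − 1 doses and can lose at most 29 − *d* of the 28.

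- *d* = 22: 21 doses taken, at most 7 lost, minimum met.
- *d* = 21: 20 doses taken, at most 8 lost, minimum missed if ibrutinib is not restarted within the cycle.

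Since 28 − 21 = 7, the hold must start by day 21 and cost 8 or more doses. Earlier missed doses widen the window: with three already missed, a hold from day 24 leaves 23 − 3 = 20 doses and the minimum is missed.

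**4. Effect on the tally.** Let *p* be the true cycle-1 DLT rate, and *f* and *g* the shares of DLT and non-DLT subjects who miss the minimum. None of these is in the documents; the values below are assumptions. The rate among evaluable subjects is

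*p*(1 − *f*) / [*p*(1 − *f*) + (1 − *p*)(1 − *g*)].

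For *p* = 1/3, *f* = 0.25, *g* = 0: (0.3333 × 0.75) / (0.3333 × 0.75 + 0.6667) = 0.25 / 0.9167 = 0.273.

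| *f* | *g* | *p* = 1/3 reads | *p* = 0.20 reads |
|---|---|---|---|
| 0.25 | 0 | 0.273 | 0.158 |
| 0.50 | 0 | 0.200 | 0.111 |
| 0.25 | 0.10 | 0.294 | 0.172 |
| 0.50 | 0.20 | 0.238 | 0.135 |
| 0.25 | 0.25 | 0.333 | 0.200 |
| 0.25 | 0.40 | 0.385 | 0.238 |

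The tally is low only when *f* exceeds *g*. Equal shares give no bias, and a larger *g* pushes it up.

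**The case against.** The conflict between the definitions is hard to dispute; the resistance is to the evaluability half.

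- **The sentence may not mean exclusion.** It sets a minimum exposure and does not say that a subject who already has a DLT is removed. The 3.1.1 drawing is not shown and may hold an exception, a cohort rule or a replacement rule. This stands as a limit on what can be known. It does not change what Section 5.2.1 says as written.
- **The overlap with ibrutinib holds is partial.** A manageable Grade 3 non-hematologic DLT is not a listed hold trigger in 5.3.1.4. The nivolumab toxicity tables in 5.3.4 hold or stop nivolumab, not ibrutinib. Table 1 allows a restart at the original dose after a first occurrence. All of this is correct and narrows the reach. It leaves the long hold or early permanent stop, which Sections 5.3.1.4 and 9.2 foresee.
- **The rate table rests on assumed inputs.** That is true. It shows direction and possible size, not an estimate.
- **The causality wording changes no classification.** Both scales can be read as counting everything from possible upward. This stands: the mismatch is a minor wording point.
- **Other safeguards exist.** The synopsis gives ongoing committee review of adverse events. Section 12.4 adds investigator meetings at least monthly and monthly committee review of related SAEs. None of these depends on DLT evaluability. The safety population (10.4.1) and the efficacy rule (10.3, 10.5) do not use DLT status. This limits the consequence and is why the point is not graded higher.

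**Conclusion.** Both halves hold, and the plan should be corrected. The definition conflict is visible in the text whatever the missing drawing contains, and it has no fixed direction. The evaluability gap rests on the sentence being applied as written and on no exception appearing in the drawing.

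The effect on a dose decision cannot be computed: no cohort size, threshold or replacement rule is readable, and the schema footnote ties de-escalation only to interim toxicities. The effect on the evaluable DLT rate depends on how often DLT and non-DLT subjects miss the minimum, which is unknown. The requirement of one nivolumab dose is not criticised, since that dose is normally given at the Cycle 1 Day 1 visit (Section 8.2.1). Confidence is medium, mainly because of the missing drawing.

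**What to change.** 1. Reconcile Sections 3.1.1 and 5.2.1 to a single DLT definition and state it once. Which events count is for the sponsor to decide. Express attribution in the categories of Section 11.1.4.
2. State in 5.2.1 that the 3-week ibrutinib minimum applies only to subjects without a DLT, so that a subject with a cycle-1 DLT stays in the tally. If the schema already says so, repeat it in 5.2.1.
3. State whether 3 weeks means dosing days. Leave the one-nivolumab-dose condition as it is.

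The cost is a few sentences in a protocol amendment, with no extra patients or tests. The downside is that the DLT count may be higher.
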